8.2.5. Physician assessment of the need for debridement at end of treatment

There are two possible outcomes for this endpoint:

- “Yes”, which is assigned if the Subject needed wound debridement after the completion of treatment.
- “No”, which is assigned if the Subject did not need wound debridement after the completion of treatment.

Based on the mITT analysis set, the number and percentage of Subjects with each possible outcome (Yes/No) will be summarized by treatment groups (VFCC and NPWTi-d vs collagenase ointment) and overall. Fisher’s exact test will be performed to evaluate the difference between the two treatment groups.

If appropriate, the analysis above will be repeated on the ITT (without imputation) and per protocol (PP) analysis sets as supportive/exploratory analyses of this secondary endpoint.

8.3. Exploratory Analysis

8.3.1. Tissue Typing Assessments

Tissue typing assessments will be summarized across timepoints by treatment arm and by visit based on the mITT and FAS (with imputation) analysis sets.

The variables to be summarized are as follows: Viable B/L/C/T (bone/ ligament /cartilage/ tendon); Viable fat; Granulation; Viable muscle/fascia; Non-viable B/L/C/T; Non-viable fat; Non-viable muscle/fascia; Eschar; and Slough. These variables will be summarized as percent of total wound surface area (%) and absolute area (cm²).

The composite variables to be summarized in terms of percent of total wound surface area (%) and absolute area (cm²) are:

1. clean/healthy/viable tissues (sum of the first four categories listed previously: viable B/L/C/T (bone/ligament/cartilage/tendon); viable fat; granulation; viable muscle/fascia) and
2. non-viable tissue (sum of non-viable B/L/C/T; non-viable fat; non-viable muscle/fascia; eschar; and slough).

Summaries by wound type (pressure ulcer, diabetic foot ulcer, venous leg ulcer and burn wounds) will be carried out if appropriate.

All data supporting the summaries will be provided as subject listings with all available and imputed data included.

8.3.2. Repeated Measures Analyses

In addition, a repeated measures analysis of covariance model (ANCOVA) will be applied to analyze the endpoints of percent of wound bed clean/viable/healthy, total wound volume and total wound area. Fixed covariates of clinical site, treatment arm, wound undermining measurement, visit, and treatment by visit. If clinical site or treatment by visit is not statistically significant, then the non-significant term(s) will be removed from the model, and the updated model will be re-run. Covariance structure will be unstructured, AR(1) or TOEFL, selected based on best fit (likelihood ratio tests or based on appropriate fit statistics).

These endpoints will be summarized based on the mITT and the FAS (with NOCB/LOCF imputation) analysis sets.

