4.1.3. Exploratory Endpoint(s)

The exploratory endpoints for this study include:

- Repeated measures of the change in percent of clean, healthy, viable tissue (%) over time, analyzing the rate of change and differences at study visits.
- Repeated measures of the percent change in total wound volume (%) over time, analyzing the rate of change and differences at study visits.
- Repeated measures of the percent change in total wound area (%) over time, analyzing the rate of change and differences at study visits.
- The absolute change from baseline to Day 6-9 upon the final dressing removal in the wound bed surface area (cm^2) considered to be clean, healthy, and viable.
- The absolute change from baseline to Day 6-9 in the total wound area (cm^2).
- The absolute change from baseline to Day 6-9 in the total wound volume (cm^3).
- Repeated measures of the absolute change in total wound volume, total wound area and viable wound area over time, analyzing the rate of change and differences at study visits.
- The percent change and absolute change of granulation tissue from baseline to Day 6-9 upon the final dressing removal
- Number of treatment applications and/or dressing changes per Subject (i.e., collagenase ointment applications versus VFCC applications); analyzed by treatment duration, wound size, and/or wound type, as appropriate.
- Total time to perform treatment applications and/or dressing changes per Subject; analyzed by wound size and/or wound type, as appropriate.
- Within-VFCC-treatment changes in the percent of wound bed surface area considered clean, healthy, viable tissue (%) at Day 2-3 and Day 4-6 study visits relative to baseline.
- Within-VFCC-treatment changes in the percent of total wound area (%) at Day 2-3 and Day 4-6 study visits relative to baseline.
- Within-VFCC-treatment changes in the percent of wound volume (%) at Day 2-3 and Day 4-6 study visits relative to baseline.

- Within-Collagenase-control-treatment changes in the percent wound surface area considered clean, healthy and viable; changes in percent wound area; and changes in percent wound volume at all study visits relative to baseline.

In addition to these exploratory endpoints, the following data will be collected from Subjects in one of the groups:

- Total number of collagenase ointment tubes used per Subject; analyzed by treatment duration, wound size, and/or wound type, as appropriate.

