12. REVISION HISTORY

The purpose of this appendix is to describe modifications made to this document. The final SAP V1.0 was written using a legacy KCI template and approved via DocuSign on 03August 2020. The changes described below cover the conversion to the current 3M SAP template and other changes to the content of the original document.

Revision History Table		
Ver- sion #	Description of change including section number impacted	Reason for change
1	Release	Initial Version
1	Deleted appendix that detailed the planned Tables, Listings and Figures (TLFs) for the final study report.	Copied planned TLFs into a separate word document. This is a communication tool for the biostatistician, statistical programmer, and other stakeholders that is not needed in ENOVIA.
1	Section 3.4 Blinding covers the blinding of independent assessor in assessing wound images and blinding of the biostatisticians and programmer prior to interim analysis.	Document all blinding occurring in this study.
1	Section 4.1.1 Modified the primary endpoint statement from: “percent change in the wound bed surface area (cm ²) considered to be clean, healthy, and viable from baseline to Day 6-9 upon the final dressing removal” to the following: “change in the percent of wound bed surface area (cm ²) considered to be clean, healthy, and viable from baseline to Day 6-9 upon the final dressing removal”.	We not computing a percent change but computing a difference or change in the derived percent of wound surface area considered clean, healthy, and viable.
1	Section 4.1.2 Added the following endpoints: change in percent of clean, healthy viable tissues, and percent change in total wound area and wound volume at interim visits relative to baseline, and not just at end of study (Day 6-9) relative to baseline. Added within-VFCC-treatment arm testing at 6-9 day visit relative to baseline for the same endpoints we are testing for between-treatment-arm differences.	To evaluate potential differences detected at interim visits (Day 2-3 and Day 4-6); and to evaluate potential differences of within-VFCC-arm testing.
1	Section 4.1.3 Added exploratory analysis on using repeated measures analyses of the primary and secondary endpoints;	To add important detail to account for

Revision History Table

Ver-sion #	Description of change including section number impacted	Reason for change

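### SAP 8.3.2 names wound levels as the repeated-measures response where SAP 4.1.3 names changes from baseline; read literally, its arm contrasts compare wound size and can lose much of their power for area

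*SAP*

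**What the plan says.** SAP 4.1.3 lists the repeated-measures endpoints. For viable tissue: "Repeated measures of the change in percent of clean, healthy, viable tissue (%) over time, analyzing the rate of change and differences at study visits". For volume: "Repeated measures of the percent change in total wound volume (%) over time, analyzing the rate of change and differences at study visits". For area: "Repeated measures of the percent change in total wound area (%) over time, analyzing the rate of change and differences at study visits". On the absolute scale: "Repeated measures of the absolute change in total wound volume, total wound area and viable wound area over time". All four are changes from baseline. SAP section 12 describes the addition in the same sense: "Added exploratory analysis on using repeated measures analyses of the primary and secondary endpoints". The primary and secondary wound-measurement endpoints are themselves changes.

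SAP 8.3.2 specifies the model. Its response is described in the words "to analyze the endpoints of percent of wound bed clean/viable/healthy, total wound volume and total wound area", with no mention of change. The terms are: "Fixed covariates of clinical site, treatment arm, wound undermining measurement, visit, and treatment by visit". The removal rule is: "If clinical site or treatment by visit is not statistically significant, then the non-significant term(s) will be removed from the model". The section gives no formula or code, no baseline value of the response, and no statement on whether the Day 0 image counts as a visit.

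The neighbouring sections are more explicit. SAP 8.2.2 and 8.2.3 define percent change in area and volume by formula and list baseline total wound area as a potential covariate. Protocol 8.3.4 uses the same model terms as SAP 8.3.2, but for the percent-change primary endpoint.

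**The concern.** A programmer working from SAP 8.3.2 alone would put the area, volume or percent viable at each visit on the left-hand side. The arm difference at a visit, or the arm main effect, then has equal mean wound size as its null hypothesis. The question in 4.1.3 is whether the change differs.

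Eligible wounds run from 16 cm² to just under 20 cm across. Between-wound spread in size may therefore be large compared with what changes in 6-9 days. Without a baseline term that spread stays in the error, and a chance size imbalance at entry carries through to every visit. The exploratory results could then appear to disagree with the area and volume results of SAP 8.2.2 and 8.2.3 for reasons unrelated to treatment.

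**Working it through.** **Inputs from the documents.** Difference 20 points (40% against 20%), SD 22 and 23 evaluable per arm (Protocol 8.4.1, SAP 6.2); two-sided test, here at 0.05. These figures belong to the primary endpoint. They are borrowed for area as an assumption, because the documents give no effect, SD or correlation for area or volume.

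**The plan's own figure.** For the Wilcoxon test, P(X<Y) = Φ(20/(22√2)) = 0.740. Noether's formula gives n = (1.96 + 0.84)² / (6 × 0.240²) = 22.7, so 23 per arm, with power 0.804. The stated 23 and approximately 80% are reproduced. A t-test on change with 23 per arm has power 0.854, which is the reference below.

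**Level against change.** Let ρ be the correlation between visits, equal for all pairs, with constant variance. A change SD of 22 implies a level SD s = 22/√(2(1−ρ)). The noncentrality at Day 6-9 is 20/(s√(2/23)).
- ρ = 0.5: s = 22.0, noncentrality 3.08.
- ρ = 0.8: s = 34.8, noncentrality 1.95.
- ρ = 0.95: s = 69.6, noncentrality 0.97.

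If arm-by-visit is dropped, the arm term averages over visits. With the effect building linearly (6.7, 13.3, 20), the average over the three post-baseline visits is 13.3, with SD s√((1+2ρ)/3). The like-for-like average *change* has SD s√((1+2ρ)/3 + 1 − 2ρ) = 22√(2/3) = 18.0 at every ρ, so its power is 0.69 throughout. If baseline is also a visit level, the average effect is 10, with SD s√((1+3ρ)/4).

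| Power | ρ 0.3 | 0.5 | 0.7 | 0.8 | 0.9 | 0.95 |
|---|---|---|---|---|---|---|
| Day 6-9, change | 0.85 | 0.85 | 0.85 | 0.85 | 0.85 | 0.85 |
| Day 6-9, level | 0.95 | 0.85 | 0.65 | 0.48 | 0.27 | 0.16 |
| Arm term, level, post-baseline visits only | 0.90 | 0.69 | 0.41 | 0.28 | 0.15 | 0.10 |
| Arm term, level, baseline as a visit | 0.74 | 0.48 | 0.26 | 0.18 | 0.11 | 0.08 |
| Day 6-9 minus baseline, arm-by-visit kept | 0.85 | 0.85 | 0.85 | 0.85 | 0.85 | 0.85 |

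The level contrasts on post-baseline visits lose power only when ρ exceeds 0.5. The last row is the arm difference in absolute change, so nothing is lost there.

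**Area, with a multiplicative effect.** Simulation with 1,500 trials per row. Assumed baseline area is lognormal, median 45 cm², truncated at 16 cm². Mean percent change is −5% for control and −25% for VFCC, SD 22.

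| CV of area | Baseline-final correlation | Raw Day 6-9 area | Absolute change | Percent change |
|---|---|---|---|---|
| 0.4 | 0.79 | 0.379 | 0.765 | 0.856 |
| 0.6 | 0.86 | 0.235 | 0.710 | 0.855 |
| 0.8 | 0.90 | 0.167 | 0.640 | 0.848 |
| 1.0 | 0.92 | 0.139 | 0.581 | 0.867 |

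**The removal rule.** Simulation with 4,000 trials per setting, median 40 cm², log-SD 0.4/0.6/0.8, baseline as a visit. The omnibus arm-by-visit test is significant in 61/53/45% of trials, so the term is deleted in 39/47/55%. Following the rule through gives 31/18/12% power, against 85-86% for percent change at Day 6-9. The one-degree-of-freedom Day 6-9-minus-baseline contrast, if kept, has 77/70/62%.

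**Percent viable.** With 20 against 40 points, SD 22 and baseline SD parameter 15-20, the level test has 63-71% power against 83-86% if change is unrelated to baseline. At a change-baseline correlation of −0.3 it has 79-84% against 84-86%. At −0.5 there is no loss.

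**Type I error.** With no arm difference, the simulated tests rejected in about 4-5% of trials. Site and undermining were not simulated, and neither was volume.

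**The case against.** The strongest reply is that 8.3.2 is shorthand. It refers to endpoints, 4.1.3 defines those endpoints as changes, the revision history says the same, and Protocol 8.3.4 pairs these terms with percent change. That stands as a plausible reading. A reader might infer that the SAP has settled on raw wound size as the response; the documents do not support that. They support only that two sections disagree and that the one specifying the model uses the wrong words.

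A reader might also infer that no contrast in the model tests change. That goes too far. Day 0 images exist and 8.3.2 does not exclude them as a visit level. If they are included and arm-by-visit is kept, the Day 6-9-minus-baseline contrast is the arm difference in absolute change, which is itself a 4.1.3 endpoint. It is not percent change, and the removal rule can delete it, so this defence is conditional.

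Nor is the analysis biased. Randomisation makes the raw arm difference an unbiased but noisy estimate, and a chance size imbalance is covered by the type I error rate.

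Finally, SAP 8.2 already tests between-arm change at each visit, with Holm control and potential baseline covariates. That limits the consequence. It does not make 8.3.2 consistent with 4.1.3.

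**Conclusion.** The inconsistency is real and should be corrected before database lock. Its cost is conditional. If the levels are modelled and the arm effect is read from a single visit or the main effect, power for area falls substantially once baseline and follow-up size correlate at about 0.8 or more. Such a correlation is plausible over 6-9 days given the range of eligible sizes, but the documents do not state one. The same is plausible for volume but untested. For percent viable the loss may be small or nil.

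The harm is lost precision and a muddled interpretation in an exploratory analysis. Nothing here touches the primary analysis or the change-based secondary tests.

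**What to change.** In SAP 8.3.2:

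- Name the response as the 4.1.3 variables at Day 2-3, Day 4-6 and Day 6-9: change in percent viable, percent change in total area and in total volume, and the absolute changes in volume, area and viable area.
- Add each variable's own baseline value and its interaction with visit as covariates.
- Keep arm-by-visit regardless of significance. Without this, the by-visit comparison can be deleted by the current rule.
- Report the arm difference in change at each visit from that model.

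The cost is a few lines of SAP text and a changed model statement. The change variables are already defined in SAP 8.1, 8.2.2, 8.2.3 and 8.3.4 to 8.3.6. The only statistical downside is a few degrees of freedom: with three visits, one for baseline and two for its interaction with visit, plus those for the retained arm-by-visit term.

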## **8.4. Additional Statistical Details**

### **8.4.1. Sample Size Determination**

Sample size determination is based on the primary endpoint. It was estimated that slough reduced by almost 20% in the Tender Wet 24 group and 10% in the Irixol N group in M. Konig et al. Assuming a 20% increase in clean, healthy, viable wound bed surface area in the collagenase ointment group and a 40% increase in clean, healthy, viable wound bed surface area in the VFCC and NPWTi-d group, and a common standard deviation of 22%, 23 evaluable Subjects per group will provide approximately 80% power to detect a statistically significant difference using the Wilcoxon Rank-Sum test (n Query Advisor® 7.0).

It is possible that some wounds assessed by the independent assessor will not meet the baseline requirement of no more than 2/3 area of a clean, healthy, viable wound bed as

measured by a 3D camera, even though the investigator assessed the wound at  $\leq 2/3$  area of clean, healthy, viable wound bed. Such Subjects will be excluded from the mITT for the analysis of the primary endpoint. To allow for this possibility, plus the possibility that some Subjects may be lost to follow-up prior to their post-baseline assessment at the Day 6-9 visit, the sample size is increased to a total of 60 randomized Subjects (ie, 30 Subjects per arm).

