3.2. Schedule of Events

A detailed schedule of events for the study is provided in Table 1.

Table 1: Schedule of Events

Procedure Description	Visit 1 Screening Day -10 to 0	Visit 2 Random- ization Day 0	Visit 3 ¹ Day 2-3	Visit 4 ¹ Day 4-6	Visit 5 ¹ End of Treatment Day 6-9	Un- scheduled
Informed Consent	X					
Inclusion/Exclusion Criteria	X	X ²				
Demographics and Subject Characteristics	X					
Medical and Surgical History	X	X ³				
Laboratory Assessment for Pregnancy	X					
Wound Assessments	X	X ⁴	X	X	X	X
Bedside Eschar Debridement (if needed)		X				
Initial Treatment Application		X				
Dressing Change			X ⁵	X ⁵		X ⁵
Dressing Removal					X	X ⁶
3D Imaging		X ⁴	X	X	X	X
End of Study					X	X ⁶
Concomitant Medication		X	X	X	X	X
Adverse Events		X	X	X	X	X

¹ Visit should not occur prior to 48 hours from the previous visit.

² Inclusion/Exclusion Criteria will be reconfirmed immediately prior to randomization if Visit 1 and Visit 2 are on different dates.

³ If the screening visit and randomization occur on different days, the medical and surgical history will be updated (if changes have occurred).

⁴ For patients undergoing eschar debridement prior to randomization, the procedure is performed before and after debridement (see Section 4.10).

⁵ Dressing changes can occur daily for patients randomized to the collagenase ointment group (or more frequently if dressings become soiled).

⁶ If the Subject is withdrawn early.

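### In the exploratory repeated-measures model, two of the three candidate covariance structures assume equal variance at every visit, so its visit-specific arm contrasts can be miscalibrated (minor)

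*SAP*

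**What the plan says.** SAP 8.3.2 adds a repeated-measures ANCOVA for percent viable wound bed, total wound volume and total wound area. Its terms are site, arm, undermining, visit and treatment by visit, and it is run on the mITT and imputed FAS sets. On covariance it says: "Covariance structure will be unstructured, AR(1) or TOEFL, selected based on best fit (likelihood ratio tests or based on appropriate fit statistics". It names no single criterion, heterogeneous-variance structure, robust standard error or order of fallback. It also has a term-removal rule: "If clinical site or treatment by visit is not statistically significant, then the non-significant term(s) will be removed from the model".

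SAP 4.1.3 states the purpose for each of these endpoints as "analyzing the rate of change and differences at study visits".

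The analysis is exploratory in the SAP. The SAP primary analysis (8.1) is a PROC MIXED model for the single Day 6-9 change, with Kenward-Roger degrees of freedom and no repeated covariance. Protocol 8.3.4 had made a repeated-measures ANCOVA the primary analysis and named no covariance structure. SAP 8.3.2 is therefore the only place where one is specified.

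**The concern.** An arm contrast at one visit needs the residual variance at that visit. With three post-baseline visits, unstructured has six covariance parameters and gives each visit its own variance. Toeplitz has three parameters and AR(1) has two, and both force one common variance.

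If SDs rise over time, the common value is too small for Day 6-9 and too large for Day 2-3, so the first test is liberal and the second conservative. If SDs fall, the reverse holds. Choosing by fit protects only if the criterion detects the difference, and about 46 subjects give limited ability to do so. Because the criterion is left open, the same data can also yield different p-values under AIC and BIC.

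At stake is the calibration of exploratory visit-specific p-values and intervals. Readers who know the protocol's original primary model will look at this output.

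**Working it through.** **Inputs from the documents.** Protocol 8.4.1 gives "a common standard deviation of 22%, 23 evaluable Subjects per group will provide approximately 80% power" and a 20-point difference (20% against 40%), planned for a "statistically significant difference using the Wilcoxon Rank-Sum test". Allocation is 1:1, tests are two-sided, and there are three post-baseline visits. No alpha is allotted to this analysis, so nominal 5% is used.

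**The plan's own figure.** P(X<Y) = Φ(20/(22√2)) = Φ(0.643) = 0.740. Noether's formula gives N = (1.960 + 0.842)² / (3 × 0.2398²) = 45.5, or 23 per arm. Power at 23 per arm is 80.4%. The stated figure reproduces, so 23 per arm and SD 22 are used below.

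**Assumptions.** The documents give no SD by visit and no correlation. Day 6-9 SD is fixed at 22, the earlier SDs vary, and the adjacent-visit correlation is 0.5 or 0.7.

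**Step 1: a common variance used outright.** Pooled SD ≈ √[(s₁² + s₂² + s₃²)/3]. The approximate error at Day 6-9 is 2[1 − Φ(1.96 × pooled/22)]. For 18/20/22, pooled = √[(324 + 400 + 484)/3] = 20.07. The ratio is 0.912, so the standard error is about 9% too small. The effective cut-off is 1.788 and the error is 7.4%. At Day 2-3 the ratio is 20.07/18 = 1.115 and the error is 2.9%.

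**Step 2: after selection.** Simulation under no arm difference with 23 per arm, complete data and arm-by-visit means kept. REML fits of the three structures were compared by AIC, AICC, BIC or sequential likelihood ratio test (LRT), with 40,000 runs per key scenario. Site, undermining and missing data were left out.

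| SD at Day 2-3 / 4-6 / 6-9 | Common variance outright (step 1) | Selected by AIC, AICC or LRT | Selected by BIC |
|---|---|---|---|
| 22/22/22 | 5.0% | 4.9-5.2% | 4.9-5.2% |
| 20/21/22 | 6.1% | 6.0-6.2% | 6.0-6.2% |
| 18/20/22 | 7.4% | 6.6-7.3% (all criteria) | 6.6-7.3% (all criteria) |
| 16/19/22 | 8.8% | 6.3-6.6% | 7.9-8.0% |
| 14/18/22 | 10.3% | 5.4-6.0% | 7.2-7.9% |
| 11/17/22 | 12.4% | 5.1-5.4% | 5.3-6.0% |
| 26/24/22 | 3.2% | 3.3-4.0% (all criteria) | 3.3-4.0% (all criteria) |

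Unstructured fixed in advance rejected in 4.9-5.2% of runs in every SD scenario.

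**Step 3: why selection only partly protects.** At 18/20/22, unstructured was chosen in 3-29% of runs, depending on criterion and correlation. At 16/19/22 it was chosen in 46-61% with AIC, AICC or LRT and in 12-18% with BIC. With a steep rise it is nearly always chosen, and the error returns to about 5%.

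**Step 4: the other direction.** In a separate run of 3,000 at correlation 0.7, the Day 2-3 test after selection rejected in 3.1-4.7% at 18/20/22 and 16/19/22.

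**The case against.** Several points on the other side stand.

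- **Reach.** A reader might infer that the trial's main Day 6-9 comparison is tested at 6-8%. It is not. SAP 8.1 fits Day 6-9 alone, and SAP 8.2.1 repeats that model at Day 4-6 and Day 2-3. Neither those models nor the other Holm-family tests use the covariance sentence in 8.3.2.
- **Direction.** A reader might infer that the Day 6-9 test must be liberal. That needs a moderate rise in SD, which the documents do not report. The endpoint is a bounded percentage, so a ceiling could compress late variance, and the test would then be conservative.
- **Term removal.** Treatment by visit is dropped if non-significant, which happens in about 95% of runs under the null. The model then reports one common arm effect, whose error was about 5.2-5.6% with Toeplitz forced. The visit contrast arises only if the term is kept or the contrast is reported anyway, as SAP 4.1.3 suggests. In a check with approximate degrees of freedom, the two-step procedure as a whole rejected in 5.8-7.4% at 18/20/22 and 16/19/22, and in 5.4-5.8% with equal variances. Part of that excess belongs to the removal rule.
- **Criterion.** The 8% needs BIC. The SAP names only likelihood ratio tests and otherwise says fit statistics.
- **Spacing.** A reader might add that AR(1) misreads unequally spaced visits. The schedule does not show this: the window midpoints are Days 2.5, 5 and 7.5, which are equal gaps. The stated rule, "Visit should not occur prior to 48 hours from the previous visit", sets only a minimum.
- **Timing.** The candidate list and approach are set out in a SAP that is to be endorsed before database lock. What remains open is which statistic decides.

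None of this defends the common-variance candidates. It limits how far the consequence reaches.

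**Conclusion.** The concern holds as a minor point about an exploratory analysis. Two of the three listed structures cannot give a visit-specific variance, and at this sample size best-fit selection does not reliably avoid them when SDs differ moderately.

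For the Day 6-9 contrast the cost is roughly one to two points of type I error with a moderate rise in SD, up to three with BIC. With falling SDs the test loses one to two points and is conservative. With equal SDs there is no cost, and with a steep rise almost none, apart from up to one point with BIC. These sizes rest on assumed SDs and correlations, complete data and treatment by visit kept. That unstructured holds about 5% does not depend on which SD pattern is true. No primary or Holm-controlled conclusion changes.

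**What to change.** In SAP 8.3.2, replace the covariance sentence with:

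> An unstructured covariance with Kenward-Roger degrees of freedom will be used; if it does not converge, heterogeneous Toeplitz, then heterogeneous AR(1), will be used in that order.

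Delete selection by best fit, which also removes the *TOEFL* misprint.

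The cost is SAP wording only. The model carries a few more covariance parameters (six, against three for Toeplitz and two for AR(1)), negligible with three visits and about 46 subjects. Kenward-Roger is already used in SAP 8.1. The change corrects the visit contrasts. It does not address the term-removal rule.
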